Pi:	[name]
Mail:	[name]
	[name]
[contact]
Email:	[contact]
Site:	Fox Chase Cancer Center
Contact:	[name] MD MSCE
Pi:	[name]
Mail:	[name]
	[name]
[contact]
Email:	[contact]

Management of Information for Multi-Center Research

Reporting unanticipated problems involving risks to participants or others: An Adverse Event is any untoward medical occurrence in participants or clinical investigation subject who was administered a medicinal product and which does not necessarily have a causal relationship with this treatment. An AE can therefore any unfavorable and unintended sign (including an abnormal laboratory finding, for example), symptom, or disease temporally associated with intervention. As per our knowledge, there are no known AEs due to intervention. The AEs will be closed monitored and recorded under the direction of Drs. [name], [name], and [name] (co-Investigators). All unanticipated problems at the Fox Chase Cancer Center will be monitored by [name] who will then communicate with the study principal investigator, [name]. Additionally, Drs. [name] and [name] will monitor the unanticipated problems involving risks to participants or others at the PVAMC. The following AE information will be collected: 1. Severity. 2. Relationship to the intervention. 3. Whether or not it is considered serious. Note the distinction between severity and seriousness. A severe AE is not necessarily serious. For Example, a headache may be severe in intensity, but would not be classified as serious unless it met one of the criteria listed below. Criteria for serious adverse event: a. Results in death, b. Is life-threatening; c. Requires inpatient hospitalization or prolongation of existing hospitalization; d. results in persistent or significant disability or incapacity. All continuing adverse events will be reported at each subsequent study visit until resolution. The date and time when the adverse even began and ended will be recorded so that the adverse even duration can be estimated. Scoring of adverse is performed by a physician who is guaranteed blinded to the treatment modality.

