
or BT; 10-20% undergo PT. The urology clinic at PRINCIPAL INVESTIGATOR (LAST, FIRST, MIDDLE): [name] PCORI Research Plan: Research Strategy 9 the Hospital of the University of Pennsylvania (HUP) treats more than 60% of this group; the rest are treated at Presbyterian Medical Center and Pennsylvania Hospital. Additionally, UPHS has a proton therapy center, providing a unique opportunity to study this new technology. The Philadelphia Veterans Administration Medical Center (PVAMC) cares for 33,000 veterans in Philadelphia area and evaluates ~400 patients with newly diagnosed PCa each year. Fox Chase Cancer Center evaluates ~500 patients with newly diagnosed PCa each year. Together, UPHS, PVAMC, and Fox Chase Cancer Center provide care to socio-demographically diverse population of ~2,500 men newly diagnosed with PCa each year. Thus, our study sample requirement of 720 patients (33% of the available pool) can be fulfilled comfortably, as demonstrated by the successful recruitment for our earlier studies. Recruitment: Prior to study initiation, investigators will explain the study objectives to physicians who actively treat PCa at the UPHS, PVAMC, Fox Chase urology clinics. During a patient's initial visit, Drs. [name], [name], or [name] will briefly introduce the study to the patient. Each week, the research assistant will contact the participating physician offices to obtain contact information for those patients who have expressed an interest in the study. Potential participants will be contacted during their office visits, at which time those eligible may agree to participate and provide informed consent, request additional information and/or time to think or request to be contacted later. Patients who request to be contacted later will be sent study information, a consent form and a prepaid return envelope. Participants will discuss the consent form with research assistant prior to signing, at which time all questions will be answered. During enrollment, compensation of \$20 will be provided. Using a similar recruitment strategy in our prior PCa studies, we had achieved enrollment and retention rates of 85% or higher. The expected number of 60 participants in each treatment group (AS, RP, RALP, EBRT, BT or PT) will be achieved as follows: (1) each recruited participant randomly assigned to the conjoint analysis intervention group will meet with research assistant to complete the computer-based conjoint analysis tasks and other surveys before initiation of treatment or making a treatment decision; (2) after treatment decision is made, patients (both cases and controls) will be assigned to the appropriate group based on treatment; (3) this process will continue until we reach the required number of participants in each group. To achieve this, we may evaluate and obtain baseline data including conjoint tasks from patients in excess of the required 360 participant each in the intervention and control groups. Based on our prior prospective cohort studies, to fulfill sample requirement of 60 participant in each treatment group ($60 \times 2 \times 6 = 720$), allowing for attrition we expect to obtain baseline assessment including conjoint tasks for 800 participants (10% excess). The cohort that does not get assigned for further follow-up due to targeted group enrollment accrual will be analyzed to ensure comparability. D.2.2 Process of stratified randomization: We will recruit 720 participants stratified by three hospitals-UPHS, PVAMC, or Fox Chase Cancer Center (Figure 3). [name] will create randomization sequences for each hospital using a pseudo-random number generator with random blocking and will place the treatment assignments in sealed, opaque envelopes. All investigators, staff and referring physicians will be masked to the treatment assignment, except the research assistant who will open the envelope and notify participants of group assignment. Participants will be instructed not to reveal their group status to physicians or study personnel, except in case of emergency or if necessary for medical reason, which we believe to be unlikely. D.2.2.1 Conjoint analysis intervention The primary goal of patient-centered PCa care is to engage patients and their families in meaningful and thorough interactions with their healthcare providers to develop accurate and well-conceived treatment choice, using all available medical information appropriately, while also considering the medical, social and cultural needs and desires of the patient and family. It is important for providers to solicit patient preferences and not make assumptions about which treatment and associated side effects patients are more likely to prefer or feel is best for them. Results of conjoint analysis will be shared with the participants of the intervention group, family members, and treating physicians prior to treatment decision. D.2.2.2 Usual care controls: Participants from this group will receive usual care that consists of standard educational material about various treatment options. D.2.3 Data collection and follow-up: After obtaining informed consent, baseline data will be obtained in person prior to the initiation of treatment. Participants will meet with the research assistant to complete the PRINCIPAL INVESTIGATOR (LAST, FIRST, MIDDLE): [name] PCORI Research Plan: Research Strategy 10 computer-based conjoint analysis tasks. Patient identifiers will be removed to maintain data confidentiality. Only the PI will have access to the master files. For conjoint analysis, each participant will be asked to express his preference for attributes and attribute levels for active surveillance and five active treatments for clinically localized PCa (RP, RALP, EBRT, PT, BT) based on choice sets presented. The choices will vary based on the differing attributes of various treatments ascertained in prior work and focus groups. After pilot testing and refining the conjoint task in Phase 1, final attributes and levels will be used. Trade-offs

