After obtaining informed consent, baseline data will be obtained in person prior to the initiation of treatment. Participants will meet with the research assistant to complete the computer-based conjoint analysis tasks. Patient identifiers will be removed to maintain data confidentiality. Only the PI will have access to the master files. For conjoint analysis, each participant will be asked to express his preference for attributes and attribute levels for active surveillance and five active treatments for clinically localized PCa (RP, RALP, EBRT, PT, BT) based on choice sets presented. The choices will vary based on the differing attributes of various treatments ascertained in prior work and focus groups. After pilot testing and refining the conjoint task in Phase 1, final attributes and levels will be used. Trade-offs among treatment features will be calculated in patient-specific utilities or part-worths associated with the attribute levels in the study. For other outcomes, participants will receive the following surveys via mail within 1-2 weeks after enrollment and prior to treatment initiation: SF-36, EPIC, AUA-SI, regret scale, CES-D, MAX-PC, SWD, PSQ-18, CPS, DCS and trust scale. Demographics, health and family history, clinical covariates and cancer progression data will be collected at 3, 6, 12 and 24 month follow-up. Histological tumor grade Gleason score and PSA and annual Elixhauser comorbidity score [257-258] will be obtained from the Pennsylvania Integrated Clinical and Research Database (PICARD), a UPHS, Fox-Chase Cancer Center electronic database, and PVAMC administrative and patient HER database. Retention and survey administration: During enrollment, importance of active participation will be emphasized. All participants will complete self-administered surveys at baseline within 1-2 weeks after enrollment (prior to treatment initiation) and again 3,6,12 and 24 months post-enrollment (see Appendix for copies of instruments, consent and medical chart review form). Non-respondents will be contacted via telephone after 10 days. In case of non-response due to death, cause of death will be noted and the physician investigators will determine cause of death (PCa or non-PCa related). The PCa conjoint analysis task, DCS, CPS and trust scale will be administered at baseline only, immediately after diagnosis of PCa and before treatment decision. Procedure for Data Sharing and Modification coordination: In Phase-1 on the study, data will be generated from focus group meetings that will take place on Penn campus. Focus group data will not be shared with other sites. This data will be used to generate a conjoint analysis instrument. This conjoint analysis instrument will be administered to participants in the intervention arm at all three sites during the Phase-2 of the study. The paper copies of various instruments that all participants complete will be stored at Penn campus in a secure office. In addition, clinical data obtained through chart abstraction will also be stored at Penn campus in a secure office. All electronic data bases will be pass word protected and only the study personal will have access to this data. Raw data will not be shared with other sites, only results in aggregate format with de-identified information will be made available to other sites. Each site PI will be responsible for addressing modifications. Additionally, the Penn site PI [name] will have overall responsibility of tracking all modifications. In case of a reportable event at a site, the site PI will inform Penn IRB and Penn site PI regarding the reportable events. Additionally, during Phase-1 of the study, we will conduct audio/video recording of focus group meetings.

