
The following documents are currently attached to this item:

There are no documents attached for this item.

Analysis Plan

Analytic Methods General: The statistical analysis will proceed in three stages: First, we will check the data quality and carry out descriptive analyses of demographics and key outcome variables. Next, we will assess preferences using conjoint analysis and inferential analysis. For continuous outcome variables, we will check for homogeneity of errors using spread-vs.-level plots and will consider transforming variables that either are highly skewed or have variance that depends strongly on the mean. We will use methods based on general linear model (univariate and repeated-measures ANOVA, mixed models) to analyze uncensored continuous outcomes, such as generic and prostate-specific HRQoL, psychological wellbeing and satisfaction with care. For potentially censored outcome variables such as time to PSA recurrence, we will use Kaplan-Meier curves and Cox proportional hazard models. Poisson regression (zero-inflated) will be used for count data. We will use Bonferroni correction for multiple testing. We will use propensity-score and instrumental variable approach to minimize observed and unobserved bias within groups (i.e. intervention group and usual care control group). **Missing Data:** We will attempt to prevent missing data by ensuring that data collection is as complete as possible. Should there be substantial missing data, however, we will employ analysis and imputation methods to reduce bias and increase efficiency [279-282]. Based on the proportion of missing data, we will use complete-case analysis, or explore available techniques, such as standardized score imputation, simple means imputation, maximum likelihood model-based imputation, data augmentation, etc. [281]. When data are evidently non-missing at random, we will conduct explicit non-ignorable modeling and sensitivity analysis [278]. **Propensity score matching:** In observational studies, comparisons between treatment groups that do not adjust for factors associated with treatment choice may be biased. Propensity score technique offers a highly practical approach to address such bias [283]. Here, the probability of each participant being in the treatment arm (i.e., the propensity score), is estimated. Participants are sorted by their propensity scores; the sample is divided into strata based on estimated scores, the treatment effect within each stratum estimated and overall estimate computed by aggregating across strata in a weighted analysis. When the model for predicting treatment status includes all relevant covariates, within strata treatment groups will be balanced on all predictors and the overall comparison of treatment arms will have substantially lower bias. We will use a model relating PCa treatment (RP, RALP, EBRT, PT, BT or AS) to baseline factors [283-284]. To study the extent to which treatment groups are now matched, we will compare t-statistics for these covariates before and after adjusting for propensity score. This will be done separately for intervention group and usual care controls. **Instrumental variable analysis:** Another limitation of observational research is the strong potential for confounding bias, due to differences in comparison groups that are not reflected in the data (i.e., unobserved bias). The instrumental variable (IV) approach is useful in reducing this bias. This technique uses one or more observable factors that influence outcome only indirectly (the IV). This allows one to mimic randomization with different likelihoods of receiving a particular treatment [227, 285-291]. Physicians play an important role in patients treatment choice- a majority of the PCa patients report that their physicians recommendation was the most important factor in their treatment choice [11-12, 37-46, 51, 55-56, 60-64]. We will use specialty of the first physician (urologist, urologic oncologist, oncologist, radiation oncologist) who the patient saw during PCa diagnosis as an IV. We will explore other potential IVs, such as absolute distance between patients residence to the hospital where they will receive care (Hospital of University of Pennsylvania, Presbyterian Medical Center, PVAMC, Pennsylvania Hospital, or Fox-Chase Cancer Center). Validity of the IV(s) is assessed as following. First, we will use Pearsons correlation coefficient to examine the correlation between IV, primary exposure (treatment) and outcomes. We will then perform a partial F-test using a linear regression where treatment group is regressed on physician specialty along with patient attributes. For a valid IV, test statistic should be very high (e.g., physician specialty will strongly predict treatment after adjusting for covariates). Next, we will perform a partial F-test using a linear probability model in which HRQoL outcomes are regressed on specialty and patient demographic and clinical variables. For an IV to be valid, this test statistic should be very low. Finally, we will compare observable attributes across patient groups cared for by different physician specialty (initial). For the IV be valid, these groups should have comparable observable attributes. **Phase 1 Focus group analysis-development of conjoint task instrument:** The goal of focus groups is to identify attributes of PCa treatment that are most salient to localized PCa patients. This process includes following steps: (1) identifying and defining attributes; (2) assigning attribute levels; and (3) creating scenarios and choice sets. Attributes will be defined based on input from patient focus groups, literature, our prior research, and prior physician focus group. Once an attribute and its extreme values are defined, we will assign them appropriate levels. A large number of possible combinations of attributes and levels will preclude

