patients participation in this study, and may be informed of which group the patient is in if the patient chooses or if there is a medical reason to necessitate this. The research coordinator will meet with the participants at the urology and radiation oncology clinics, and the participant will know whom to contact in case of emergency. Release of participant information to other parties not affiliated with the research team will be governed by the HIPAA Privacy Rule Guidelines. Disposition of data: The raw data will be stripped of participant identifiers immediately and each participant will be assigned a unique identifier. Our unique participant identifier is a number that is incremented by one for each new consented participant accrued in the study. This identifier number is not derived or linked to the participants social security number, hospital ID number, medical record number, or some other number that can also be used to directly identify the data source. The participant identifier information will be held highly confidential and only the principal investigator will have access to it. The principal investigator will maintain a master file linking the participants medical record number and the assigned unique participant identifier. This file will be password protected on a secured computer. The data will be stored on a secure and password protected computer. Every attempt will be made by the investigators to maintain all information collected in this study strictly confidential. In any publications or presentations resulting from this research, data will be presented in aggregate format only and the participants will not be identified individually. To ensure accuracy of data while transferring raw data to computerized database, data will be verified in three steps. First, double entry will be done for raw data that are entered into a computer. Next, the principal investigator will perform a random data check. Finally a one-way frequency of all the variables will be run and checked to see if any incorrect or out of range information appears in the database. If so, the necessary corrections will be made. In order to generate the final report and publications, data will be stored for approximately four years beyond the end of the study period. Sharing Study Results: We will seek advice from institutional review and data safety monitoring board regarding sharing the study results with participants over the study duration. The published results will be made available to all the participants, caregivers and physicians. Ethical Considerations: This study will not modify a participants prescribed medical regimen in any way. The major ethical considerations involve issues of notification of physicians when participants are worsening. Since our research coordinator and research assistant are not medical practitioners, their role will be to remind the participant that they must take action if their condition is worsening (e.g. notify the physician). The research coordinator will be given guidelines by the medical co-investigators to identify extreme cases. In these instances, the investigators will contact the participants physician.

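### The blanket masking statement cannot hold for treating physicians, because they receive the intervention arm's conjoint results before the treatment decision

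*Combined protocol and SAP*

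**What the plan says.** D.2.2 (Process of stratified randomization), repeated under Subject recruitment, sets out the masking: "All investigators, staff and referring physicians will be masked to the treatment assignment, except the research assistant who will open the envelope". It adds an instruction meant to protect it: "Participants will be instructed not to reveal their group status to physicians or study personnel". The only exceptions are an emergency or a medical need, which the authors think unlikely.

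D.2.2.1 (Conjoint analysis intervention) describes delivery: "Results of conjoint analysis will be shared with the participants of the intervention group, family members, and treating physicians prior to treatment decision". D.2.2.2 gives controls standard educational material and describes no report for them. Under Procedures, the instrument is tied to one arm: "This conjoint analysis instrument will be administered to participants in the intervention arm at all three sites".

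Subject Confidentiality and Subject Privacy both say that the patient's physician has a right to know of participation and "may be informed of which group the patient is in if the patient chooses", or for a medical reason.

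The one masking safeguard attached to a specific assessment is under Management of Information for Multi-Center Research: "Scoring of adverse is performed by a physician who is guaranteed blinded to the treatment modality".

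**The concern.** The protocol claims a masking property that its own intervention removes. If the claim is carried into the trial report, readers will take outcome assessment to be protected from knowledge of the arm. Apart from adverse-event scoring, the documents describe no other protection: no arm-masked abstraction or adjudication is laid down for complications, progression, adjuvant status or cause of death.

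A second, weaker issue follows from the same facts. A physician who receives reports for some patients may also treat controls. Whatever general habit of eliciting preferences the reports encourage could reach the control arm and narrow the contrast in treatment choice under Specific Aim 3.

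**Working it through.** The point rests on no figure in the plan, so the check is a comparison of the sections.

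**1. Does a report reveal the arm?** Results are shared for the intervention group only (D.2.2.1). A physician who receives one knows the man's arm. A physician who knows that a man is enrolled, as the confidentiality text allows, and receives nothing has good reason to think he is a control, though this is not certain: a man might not have completed the task.

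**2. Does another reading remove the conflict?**
- *Referring versus treating physicians.* D.2.2 masks referring physicians, while D.2.2.1 informs treating physicians. If these were always different people, that sentence could stand. The non-disclosure instruction, however, covers physicians without qualification, so the conflict remains.
- *Who completes the task.* Parts of the Design and Subject recruitment text can be read as giving the conjoint task to all 800 baseline participants, while Procedures limits it to the intervention arm. Under either reading, only the intervention group's results are shared.

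**3. Second route.** D.2.2 allows disclosure only for an emergency or a medical reason. The confidentiality sections add the patient's own choice. The two rules differ.

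**4. How many men?** The plan randomizes 360 to each arm. The treating physician of every intervention man is due to receive results: 360 of 360, which is half of the 720.

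**5. Which roles?** Unmasking follows from the text for treating physicians. For non-treating investigators and other staff, nothing shows that they see reports. Physician investigators introduce the study at the first visit, which suggests that some may also treat participants. The names are removed from the public copy, so overlap with the outcome reviewers cannot be established.

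**6. Which outcomes?**
- *Complications* (D.2.4.3.2): identified from hospital admissions within 30 days of treatment, using lists still to be developed. Judgement is involved and no masked abstraction is stated. Clearly exposed.
- *Progression by change of stage* (D.2.4.3.1): open to judgement. Exposed.
- *Recurrence by PSA* (D.2.4.3.1): numeric rules, above 0.2 ng/ml after surgery and nadir plus 2 ng/ml after radiation, with PSA taken from electronic databases. Less exposed.
- *Adjuvant status and cause of death* (D.2.4.3.1 and D.2.3): the first is a six-month rule followed by investigator review. The second is decided by physician investigators when non-response is due to death. Neither is a listed outcome, but both are investigator judgements without stated masking.
- *Adverse events*: a blinded scorer is specified. The protocol uses the word treatment both for the trial assignment and for surgery, radiation or surveillance, so it is unclear whether the scorer is blinded to study arm.
- *Quality of life* (SF-36 and PCI, the basis of the sample size under Accrual): self-reported by men who know their arm. Physician masking would not protect it.

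**7. Is carry-over possible?** Allocation is by individual man: one investigator "will create randomization sequences for each hospital using a pseudo-random number generator with random blocking". Nothing separates arms by physician. The Analysis Plan says that "a majority of the PCa patients report that their physicians recommendation was the most important factor in their treatment choice", and Aim 3 compares the likelihood of active surveillance among low-risk men between arms. The route exists. The documents neither measure nor limit it.

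**The case against.** The best defence is that sharing results with physicians is the intervention, so their unmasking is inherent and the fault is one of wording. That is right about the design and is why the fix leaves the intervention alone. It does not rescue the masking sentence.

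Four stronger readings are tempting, and the documents do not support them.

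- *That no one is masked.* Only treating physicians are shown to be unmasked.
- *That all objective outcomes and adverse-event scoring are compromised.* PSA recurrence follows numeric thresholds, cause of death is not a listed outcome, and nothing shows that the adverse-event scorer treats the men or sees reports. What stands is the ambiguity over what that scorer is blinded to.
- *That carry-over inflates the required sample by a known factor.* If controls received a fraction c of the effect, the multiplier would be 1/(1 − c)²: 1.23 at c = 0.1 and 2.04 at c = 0.3. But c appears nowhere in the documents, and treatment choice, the outcome at issue, has no sample-size calculation to multiply. For quality of life, the plan's detectable 1.2 points would become 1.2/0.7 = 1.7 at c = 0.3, still below the plan's own meaningful changes of 5 to 9 points (PCI) and 7 points (SF-36). Moreover, each report holds one man's part-worths, which do not transfer to another; only general learning by the physician could.
- *That the statistician can simply be declared masked.* Data and Safety Monitoring has the study statistician review interim reports with the board in closed session, and the board assesses baseline comparability between groups. Arm-level access is plausible.

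**Conclusion.** The contradiction is established from the text: masking as stated cannot hold for treating physicians, for all 360 planned intervention men, and the two disclosure rules also disagree. This assumes only that results are delivered as D.2.2.1 describes.

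The consequences are narrower. Complications and stage-change progression are the outcomes most exposed, since no masked assessment is described for them. The size and direction of any bias cannot be derived from the documents. Carry-over to controls is a reasonable but unquantified limitation of the Aim 3 treatment-choice comparison, resting on individual randomization within hospital and on physicians possibly treating both arms. The point does not undermine the quality-of-life power calculation. It should be corrected because the trial would otherwise report a safeguard that it does not have.

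**What to change.** 1. Reconcile D.2.2 (and its repeat under Subject recruitment) with D.2.2.1 and with Subject Confidentiality and Subject Privacy. State that participants and treating physicians are unmasked, list which other roles are masked, and give one disclosure rule.
2. Have complications and stage-change progression abstracted, and the reviews of adjuvant status and cause of death done, by existing team members who are not the man's treating physician and who see neither his assignment nor his conjoint report.
3. State whether the adverse-event scorer is blinded to study arm.
4. Do not describe the statistician as masked unless that is confirmed.
5. Record carry-over to controls as an unquantified limitation of the Aim 3 treatment-choice comparison.

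The cost is protocol wording and allocation of abstraction and review duties; the intervention, randomization and sample size stay as they are. The documents do not say who abstracts the charts, so the team should confirm that enough people without access to arm or report are available. The downside is that the stated level of masking is lower.
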